8.2 Early closing or suspension of the study

The Promoter reserves the right to interrupt or suspend the study at any time for reasonable medical, safety, or administrative reasons.

The Sponsor will notify the Ethics Committee and the Principal Investigator of the decision to suspend or interrupt the study with the reasons. It will also provide the trial with specific instructions to inform the patients and indications on the procedures to be followed.

Circumstances that may justify interruption or suspension of the study:

- Determination of an unexpected, significant or unacceptable risk to participants
- Any serious or persistent case of non-compliance with the legislation
- Suspension or termination of Ethics Committee approval
- The feedback from the data is excessively different from that expected.

In the event of suspension, the study may be resumed once issues of safety, protocol compliance or data quality have been resolved to the satisfaction of the Sponsor and the Ethics Committee.

9. Evaluation of effectiveness

9.1 Primary endpoint

The primary endpoint of the study is the equivalence between the detection of parameters useful for the diagnosis of OSA using the SOUNDIV system and standard polysomnographic methods.

9.2 Secondary endpoint

The secondary endpoint of effectiveness of the clinical investigation is the evaluation of satisfaction with the use of SOUND I after the night of recording the parameters, through the patient's completion of a questionnaire prepared for the study.

10. Evaluation of the safety and vigilance of the medical device

The clinical investigation also aims to evaluate the safety and tolerability of the SOUNDI device by recording adverse events (secondary safety endpoint).

10.2 Definitions

Adverse Event (AE)

AE means any harmful clinical event, disease, unintentional injury or favorable clinical sign (including an abnormal laboratory result) that occurs in subjects, users or other persons as part of a clinical investigation, whether or not the event is related to the device under investigation

Note 1: This definition includes events related to the wearable wireless device (SOUNDI), polysomnography and any other procedures covered by the study protocol.

Note2: For users or other persons this is limited to events relating to the SOUNDI medical device.

Serious Adverse Event (SAE)

Serious Adverse Event (SAE) means any adverse event that has one of the following consequences:

- undeath;
- a serious worsening of the subject's health conditions which resulted in:

- (i)a life-threatening illness or injury;
- ii) a permanent damage to a body structure or function; iii) the need for hospital admission of the patient or its prolongation;
- fetal distress, fetal death or a malformation or physical or intellectual disability congenital

Note 1: A planned hospitalization for a pre-existing condition, or a procedure required by the clinical investigation plan, without serious deterioration in health, is not considered an SAE.

Adverse Device Effect (ADE)

Adverse device effect (ADE) means an adverse event related to the use of the SOUNDI wearable wireless device.

Serious Adverse Device Effect (SADE)

Serious adverse device effect (SADE) means a serious adverse effect related to the use of the SOUNDI device.

Serious and Expected Adverse Device Effect (ASADE)

Anticipated serious adverse device effect (ASADE) means an adverse effect of the device already identified in the risk analysis.

Adverse Device Effect Serious and Expected (USADE)

Serious and unexpected adverse effect (USADE, unanticipated serious adverse device effect) means an adverse effect of the device not identified in the updated version of the risk analysis.

Device defect

Device defect means any deficiency in the identity, quality, durability, reliability, safety or performance of a device under investigation, including malfunction, errors in use or inadequacy of information provided by the manufacturer.

10.3 Classification of adverse events

The investigator and/or the Promoter will provide an assessment of the seriousness, severity of the event and the causal relationship with the device under study and will also record the duration, outcome and actions taken.

10.3.1 Evaluation of the severity of the event

The intensity of the AE will be characterized as follows:

O mild: transient discomfort or mild; no activity limitations; no intervention doctor/therapy required.

O moderate: from mild to moderate limitation of activity; some assistance may be necessary; none or minimal medical intervention/therapy required.

O severe: marked limitation of activity, usually requires some assistance; intervention doctor/therapy required, hospitalization possible.

10.3.2 Evaluation of the relationship to the medical device

The relationship between the use of the medical device and the occurrence of each adverse event must be evaluated and classified. During the evaluation of causality, the investigator must use clinical judgement, including all relevant factors such as time course and latency, known properties of the device and alternative explanations (e.g. medical history, concomitant diseases) and must. Please consult relevant documents, such as instructions for use, clinical protocol or risk analysis report, as all foreseeable serious adverse events and potential risks are listed and assessed in these documents.

The Investigator and the Sponsor will separately evaluate and document the relationship between an adverse event and the experimental device or procedure, according to the following classification criteria:

- causal relationship: event is associated with the medical device or a procedure beyond any reasonable doubt
- probable: the relationship with the use of the experimental device seems relevant and/or the event cannot be reasonably explained by another cause, but additional information can be obtained.
- possible: the relationship with the use of the device is weak, but cannot be completely ruled out. Alternative causes are possible (e.g. a concomitant disease, a treatment, another device, etc.). Cases in which the relationship cannot be established or sufficient information is not available should be classified as possible.
- unlikely: the relationship to the use of the device does not appear relevant and/or the event can be reasonably explained by another cause, but additional information may be obtained.
- not related: the relationship with the medical device or procedure can be excluded.
- unclassifiable: clinical event for which the information received is inadequate and/or contradictory and do not allow reasonable ascertainment.

10.3.3 Duration of the event

For both AE and SAE, the experimenter will record the start date and time and the end date and time of the event.

10.3.4 Outcome of the event

The clinical outcome of the AE or SAE will be recorded as follows:

- death
- resolved: the patient has returned to the condition prior to the event
- ongoing: the patient has not recovered and the symptoms continue
- resolved with consequences: the patient recovered from the event, but with clinical consequences.

10.3.5 Actions Undertaking

The treatment or action taken following the onset of an AE or SA will be recorded as follows: o

- pharmacological treatment: e.g. inflammatory drugs
- or non-pharmacological treatment: e.g. physiotherapy
- or none: no treatment or action taken.

10.4 Predictable/expected adverse events and effects

Predictable potential adverse effects are exclusively linked to the use of double-sided medical adhesive and may include skin irritation, inflammation or other negative reactions.

More information on expected adverse effects and their management is available in the investigator's dossier.

10.5 Reporting of adverse events

The reporting of adverse events will comply with what is reported in the national reference legislation (DLvo37/2010), in the UNIENISO14155 technical standard and in the MEDDEV2.7/3 guidelines.

All adverse events (serious and non-serious) and medical device defects will be collected, carefully evaluated and documented in the medical record and in the CRF by the Principal Investigator.

The Investigator must immediately communicate to the Sponsor of the clinical study and in any case no more than 3 days after the event:

- a) any SAAnd b)
- any defect in a device which could have caused a serious adverse event in the absence of appropriate measures or intervention or if the circumstances had been less favourable;
- c) any new conclusions relating to each event referred to in letters from a) to c).

The communication will be made using the appropriate form to be sent to:

[contact].

Furthermore, the Investigator will have to do what is necessary for the safety and well-being of the subject, until recovery or clinical stabilization.

If/when additional information is available, the Investigator will send a follow-up SAE in the same manner and timing as the initial SAE.

10.6 Notification to the Competent Authorities

Events will be reviewed by the Promoter to determine any reporting obligations. Reporting will take place within the time limits described in the applicable regulations.

In the case of USADE, the Sponsor or its delegate will report the results of the evaluation to the Competent Authority and the Principal Participating Investigator in accordance with the applicable regulations.

The following events must be reported by the Promoter to the Competent Authorities (Ministry of

Health):

- any serious adverse event (SAE) for which there is a causal relationship, even if only reasonably possible, with the device under investigation, the comparison product or the investigation procedure;
- any defect in a device that could have caused a serious adverse event in the absence of appropriate measures or intervention or if the circumstances had been less favourable;
- any new conclusion relating to each event referred to in the previous 2 points.

The Promoter must forward the events specified above to the Ministry of Health and the Ethics Committee with the following deadlines:

- immediately and no later than 2 days in the case of SAE with imminent danger to life, death;
- immediately and no later than 7 days in other cases SAE.

10.7 Consequences on risk analysis

If serious adverse effects occur, defects in the device which could have produced a serious adverse effect, the Promoter will evaluate, together with the Principal Investigator, whether to update the risk analysis and implement preventive or corrective actions.

11. Statistics

11.1 Effectiveness analysis

The continuous variables will be reported as the mean value and standard deviation or as the median and interquartile range in the case of non-normally distributed data. Therefore, for each parameter the agreement between the measurement carried out with the SOUNDI method and the one carried out with polysomnography (gold standard) will be evaluated using the Bland-Altman graph and the Concordance Correlation Coefficient (CCC) [6]. In short, this graph represents the value of the differences of the measurements carried out with two methods differ from their average[7]. The CCC varies between -1 and 1, values between 0.61 and 0.80 indicate substantial agreement while values greater than 0.81 almost perfect agreement according to the Landis and Koch scale [8].

Descriptive statistics will be used to evaluate the subject's satisfaction with using SOUNDI.

11.2 Securityanalysis

The safety analyzes will be carried out on all patients to whom the Sound device and the polysomnography device have been applied, regardless of the validity of the data collected.

In general, safety analyzes will be descriptive in nature. The frequency, severity, severity and causal relationship of adverse events will be tabulated.

Both the number and percentage of events and patients experiencing an event will be presented. Additionally, adverse events that led to study suspension and device defects reported.

Sample size.

A sample of 50 analyzable patients will guarantee a power of 90% in determining six values of the parameters detected with the SOUND I method are in agreement with those measured by polysomnography. The estimate was made considering: i) a z-head and a tail with a significance level of 5%; ii) a value of the CCCparia 0.60 below H0; iii) a value of the CCCparia 0.81 below H1 . Sample sizing was performed using PASS2021(PowerAnalysisandSampleSizeSoftware(2021).NCSS,LLC.Kaysville,Utah,USA).

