Endpoints:	
Primary endpoint: Equivalence between the detection of parameters useful for the diagnosis of OSA using the SOUNDI system and standard polysomnographic methods.
 
Secondary endpoints:
 
 • evaluation of satisfaction with the use of SOUND I after the night of recording the parameters, by completing a questionnaire. • safety and tolerability of the SOUNDI device using it recording of adverse events.
Estimated enrollment:	50 subjects
Study population:	Adult subjects belonging to the clinical centre, to carry out a polysomnography for suspicion of a breathing disorder sleep.
Inclusion criteria and exclusion:	
Inclusion criteria:
 
 • Signature of informed consent • Patients of both sexes, of any ethnicity • Age between 20 and 70 years • Prescription, from clinical practice, to carry out a polysomnography on suspicion of a breathing disorder in sleep. 
Exclusion criteria:
 
 • Women during pregnancy • Insufficient cooperation/degree of collaboration in following the procedures required by the study • Participation in another clinical study. • Allergy to one of the materials in the device • Pacemaker users.
Procedures:	
Some data will be collected during a visit anthropometric devices will be positioned simultaneously for polysomnography:
 
 - a traditional polysomnigraph, as prescribed - the experimental Soundi device. 
During the night, at the patient's home, the following parameters will be acquired for at least 8 consecutive hours: oro-nasal flow, thoracic and abdominal respirogram, snoring, ECG, arterial oxygen saturation, body position.
 
The following morning the subject will return to the clinics to return the two systems and complete a simple satisfaction questionnaire prepared for the study.

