	
Efficacy analyzes will be carried out on all patients who have completed the evaluation and whose data will be considered evaluable.
 
For each parameter, the agreement between the measurement carried out with the SOUNDI method and the one carried out with polysomnography will be evaluated using the Bland-Altman graph and the Concordance Correlation Coefficient (CCC).
 
Statistical considerations:
 
Descriptive statistics will be used to evaluate the subject's satisfaction with using SOUNDI.
 
The safety analyzes will be carried out on all patients to whom the Sound device and the polysomnography device have been applied, regardless of the validity of the data collected. The safety analyzes will be of a descriptive nature.
 
A sample of 50 analyzable patients will guarantee a power of 90% in determining six values of the parameters detected with the SOUNDI method which are in agreement with those measured by polysomnography.

Study duration:
	
The expected duration of enrollment of all subjects is approximately 6 months.
 
The expected duration of the study for the subject is a maximum of 24 hours.
 
The overall duration of the study will be 1 year.

Summary

1. Abbreviations	9
2. Operational Background	10
2.1 Rational	10
2.2 Background	10
3. Information on the medical device Pre-clinical	11
3.1 trials Trials on healthy	14
3.2 volunteers Risks and	14
3.3 benefits	15
4. Study Design Comparison	15
4.1	15
5. Objectives of the study	16
5.1 Primary objective	16
5.2 Secondary objectives	16
6. Study population Number of	16
6.1 patients Inclusion	16
6.2 criteria Exclusion	16
6.3 criteria	16
7. Study procedures	16
7.1 Compliance with Followup	17
7.2 procedures	17
8. Duration of the study	18
8.1 Interruption and withdrawal of subjects from the clinical investigation	18
8.2 Early closure or suspension of the study	18
9. Evaluation of effectiveness	19
9.1 Primary endpoint	19
9.2 Secondary endpoint	19
10. Evaluation of the safety and vigilance of the medical device	19
10.1 Recording of adverse events Definitions	19
10.2 Classification	19
10.3 of adverse events Predictable/expected	20
10.4 adverse events and effects Reporting of adverse	22
10.5 events Notification to the Competent	22
10.6 Authorities 10.7 Consequences on risk	22
analysis	23
11. Statistics	23
11.1 Effectiveness analysis	23
11.2 Securityanalysis	23
11.3 Analysis set	24
11.4 Systematic errors - bias	24
12. Medical device	24

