6.3 Exclusion criteria

- Women during pregnancy
- Insufficient cooperation/degree of collaboration in following the procedures required by the study
- Participation in another clinical study.
- Allergy to one of the materials in the device
- Pacemaker users.

7. Study procedures

All subjects enrolled in the study will undergo polysomnography (monitoring

nocturnal cardiorespiratory for the diagnosis of apnea in sleep) with traditional polysomnography (Embletta, Natus) according to normal clinical practice and at the same time as data acquisition with the Soundi system.

On the afternoon before the night of the evaluation, at the Sleep Medicine Service clinic, each object will be placed

- a traditional polysomnigraph, as prescribed
- the Soundi experimental device.

The patient will be instructed by the Investigator on the correct management of the devices.

During the visit, the following anthropometric data will be collected: age, Body Mass Index (BMI), neck circumference and abdomen.

Furthermore, the Experimenter will program the devices to begin recording the parameters at the moment the subject expects to recharge and continue for at least 8 consecutive hours.

During the night, at the patient's home, the following parameters will be acquired with two systems: oro-nasal flow, thoracic and abdominal respirations, snoring, ECG, arterial oxygen saturation (SaO₂), body position.

The following morning the subject will return to the clinics to return the two systems which will be detached by the medical staff. There, the subject will be asked to fill out a simple satisfaction questionnaire prepared for the study.

The signals acquired with both systems simultaneously will be processed by the software RemLogic, via automatic analysis software, with subsequent manual correction by a doctor expert in sleep medicine, the following indices used, according to international guidelines, for the diagnosis of respiratory and sleep disorders:

- Apnea Hypopnea Index (AHI) total and supine
- AHI central
- AHI obstructive
- Oxygen Desaturation Index (ODI)
- Average arterial oxygen saturation (SaO₂).
- Minimum SaO₂
- Time with SaO₂ < 90%
- Average heart rate
- Minimum heart rate
- Percentages of time spent in different body positions.

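### The stated 90% power is right for one CCC test, so per parameter, but the primary endpoint is a single equivalence conclusion over several unranked indices with no rule for reaching it.

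*Protocol*

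**What the plan says.** The synopsis and the sample-size paragraph (end of section 11.2) both attach the power to the parameters as a group. The sample-size paragraph reads: "A sample of 50 analyzable patients will guarantee a power of 90% in determining six values of the parameters". The synopsis says 50 analyzable patients "will guarantee a power of 90% in determining six values of the parameters detected with the SOUNDI method" that agree with polysomnography. The words about six values look like a translation slip for *if the values*. No part of the protocol names six parameters.

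The calculation has one null value, "a value of the CCCparia 0.60 below H0", one alternative value of 0.81, and a 5% level. The garbled description of the test reads as a one-tailed z-test. No other inputs are listed.

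Section 9.1 defines the primary endpoint as "the equivalence between the detection of parameters useful for the diagnosis of OSA" with the device and with standard polysomnography, and the synopsis says the same. Neither names a parameter.

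Section 7 lists "the following indices used, according to international guidelines, for the diagnosis of respiratory and sleep disorders". The list has ten bullets. The first, "Apnea Hypopnea Index (AHI) total and supine", holds two indices, and the last, on body position, covers several percentages. That makes at least 11 indices, none marked as primary.

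Section 11.1 assesses "for each parameter the agreement between the measurement carried out with the SOUNDI method" against polysomnography by Bland-Altman graph and CCC. It adds descriptive bands for the CCC: substantial from 0.61 to 0.80, almost perfect above 0.81. It does not say how the separate results lead to the primary conclusion.

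**The concern.** Power belongs to a defined test or decision. The stated 90% comes from a test on one coefficient, while the primary endpoint is one conclusion about a set of parameters. Between the two there should be either a lead index or a rule for combining indices, and the protocol has neither.

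This matters because the study is a pre-marketing validation. If some indices agree well and others poorly, the plan as written would let the result be called equivalence or not after the event, with 90% power quoted in either case. The gap works in both directions. A demand that all indices agree lowers power below the stated figure. A willingness to accept any one raises the false-positive rate above 5%.

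**Working it through.** **Inputs from the protocol (sample-size paragraph).** N = 50 analyzable; CCC 0.60 under H0 and 0.81 under H1; 5%, read as one-sided; power 90%.

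**Step 1: reproduce the plan's figure.** On the Fisher z scale:

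- Difference: atanh(0.81) - atanh(0.60) = 1.1270 - 0.6931 = 0.4339.
- N for 90% power = ((1.645 + 1.282) / 0.4339)^2 + c = 45.5 + c. With variance 1/(n-2), c = 2 and N = 47.5. With variance 1/(n-3), c = 3 and N = 48.5. Rounded up, this is 48 or 49 patients.
- Power at N = 50 = Phi(0.4339 x sqrt(50 - c) - 1.645), which is 91.3% for c = 2 and 90.8% for c = 3.
- A simulation of normal data with N = 50 gives 90.6%.
- A two-sided 5% test would need 58 or 59 patients and give 84-85% at N = 50, so the one-sided reading is the one that fits.

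The plan's figure is therefore reproduced, and it is the power of one CCC test.

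**Step 2: compare with the endpoint.** The endpoint covers several parameters, section 7 lists at least 11 indices, and no section gives a lead index or a required number. The power of the overall conclusion cannot be calculated from the protocol, because the event that counts as success is undefined.

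**Step 3: illustrate how much the missing rule could matter.** None of the following assumptions is in the protocol: the combination rule, the number k of indices that count, and a common correlation r between the test statistics.

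*(a) All k must agree.* Each index has true CCC 0.81 and 90% power. Joint power is the integral over a standard normal u of Phi((1.282 + sqrt(r) u) / sqrt(1 - r))^k. At r = 0 this reduces to 0.90^k.

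| k | r = 0 | r = 0.5 | r = 0.8 | r = 0.9 |
|---|---|---|---|---|
| 2 | 81.0% | 83.2% | 85.6% | 86.9% |
| 11 | 31.4% | 58.1% | 73.1% | 79.0% |

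Starting from the achieved 90.8% instead of 90%, the ranges become 82-88% for two and 35-80% for 11. An all-agree rule would keep the error at or below 5%. The r = 0 figure for 11 is an extreme, since the indices come from the same night and some overlap.

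*(b) Any one suffices.* With every true CCC at 0.60, the chance of at least one false rejection is 1 - 0.95^k at r = 0. For k = 11 this is 1 - 0.569 = 43%. By simulation it falls to about 26% at r = 0.5 and 12% at r = 0.9, still above 5%.

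**The case against.** The strongest reply is that the protocol analyses each parameter separately and the power was calculated for one CCC, so the two match. On that reading the plural in the sample-size sentence is loose, translated wording, and nowhere does the text expressly claim 90% power for a joint conclusion. This stands: the per-parameter figure is correct and consistent with section 11.1. It does not answer the endpoint, which section 9.1 words as one equivalence conclusion.

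The joint-power figures also depend on assumptions, and the shortfall can vanish. If every true CCC were 0.85, all-agree power at N = 50 would be 97-98% for two indices and 86-96% for 11. This stands too, and is why those figures serve only as illustration.

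A statistical analysis plan may exist and may say how the CCCs are summarised. But the protocol itself states the primary endpoint and what the power refers to, and the mismatch lies in that text.

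Three stronger readings are tempting and not supported:

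- *The study is underpowered or its sample size is wrong.* The calculation reproduces, and no joint-success rule is stated against which 50 patients would fall short.
- *Six parameters are primary.* The only basis is the apparent translation slip.
- *The section 7 list has a wider scope than the OSA parameters of the endpoint.* Section 4 uses the OSA wording and the broader breathing-and-sleep wording for the same recordings, so the phrases appear interchangeable and the list is the natural candidate set.

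**Conclusion.** The point holds in a limited form. The 90% at N = 50 is right for one one-sided 5% CCC test, so per parameter. It is not the power of the overall equivalence conclusion named as primary endpoint, because the protocol neither names a lead index nor says which or how many indices must agree. For the same reason the 5% is not the error rate of that conclusion if a single index could carry it.

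The size cannot be fixed from the protocol. Under the hypothetical rules above, power would be 81-87% (two indices) or 31-79% (11) if all had to agree, and the false-rejection chance about 43% if any one of 11 independent indices sufficed. These figures rest on an assumed rule, count and correlation and, for the power figures, on a true CCC of 0.81 for every index.

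This should be fixed: the arithmetic needs no change, but what it refers to does.

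**What to change.** Change the synopsis, section 9.1, section 11.1 and the sample-size paragraph together, in one of two ways.

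- *Minimum:* restate the 90% and the 5% as applying to each parameter separately, and make no overall equivalence claim at that power.
- *Preferred, before endpoint data are reviewed:* name one lead primary index, chosen by the sponsor (total AHI is one example), and tie the 5% and 90% to it. Report the other indices as secondary, each with its CCC, limits of agreement and confidence intervals.

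The preferred option narrows an objective that now covers several parameters, and that choice is the sponsor's. A sponsor who wants a claim over several indices jointly would have to list them, state the rule and recalculate the sample size for it.

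Under either option N stays at 50, and data collection and the per-parameter analyses are unchanged. The cost is a protocol amendment, through the route in section 13.2 if the study has begun, and giving up a blanket equivalence claim at 90% power.

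### Does the 90% power claimed for 50 patients fail because the CCC sizing rests on normal data?

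*Protocol*

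**What the plan says.** The sample-size paragraph under section 11.2 states that "A sample of 50 analyzable patients will guarantee a power of 90"% for showing agreement between SOUNDI and polysomnography. It then lists its inputs: "a z-head and a tail with a significance level of 5"% (evidently a mistranslation of a one-tailed z test), "a value of the CCCparia 0.60 below H0", a CCC of 0.81 under the alternative, and the software used. The synopsis repeats the power figure without these inputs. Neither place names a distribution.

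Section 11.1 reports continuous variables as mean and standard deviation, "or as the median and interquartile range in the case of non-normally distributed data". It then assesses "for each parameter the agreement between the measurement carried out with the SOUNDI method" and polysomnography with a Bland-Altman graph and the CCC, read against the Landis and Koch bands. It names no hypothesis test and no confidence bound.

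The parameters are listed in section 7. They include "Apnea Hypopnea Index (AHI) total and supine", central and obstructive AHI, "Oxygen Desaturation Index (ODI"), and time with saturation below 90%. The primary endpoint in section 9.1 is "equivalence between the detection of parameters useful for the diagnosis of OSA", so these indices belong to it.

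**The concern.** The sizing formula for a CCC uses a variance that holds for bivariate normal data. Section 11.1 itself allows for non-normal data, but only in the choice of descriptive summary; the CCC is then applied to every parameter alike. Event rates and time below a saturation threshold cannot be negative, so right skew is plausible.

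Under clear skew, the CCC estimate varies more from sample to sample than the formula supposes. A z test with the normal-theory standard error would then pass a device with a true CCC of 0.60 more often than 5% of the time, and would miss a device with a true CCC of 0.81 more often than 10% of the time. A power figure presented as guaranteed would be too strong for those indices.

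**Working it through.** **Inputs.** From the sample-size paragraph: n = 50 analysable patients, one-sided 5% level, CCC 0.60 under the null and 0.81 under the alternative. From section 7: the list of parameters. The protocol gives no standard deviation, skewness or share of zeros for any index, so every shape below is an assumption.

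**Step 1: reproduce the stated figure.** On the Fisher scale, atanh(0.81) = 1.1270 and atanh(0.60) = 0.6931, a difference of 0.4339. With variance 1/(n − 2), Lin's form without shift in location or scale:

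- n = (1.645 + 1.282)² / 0.4339² + 2 = 8.567 / 0.1883 + 2 = 47.5, so 48.
- Power at n = 50: Φ(0.4339 × √48 − 1.645) = Φ(1.361) = 0.913.

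With variance 1/(n − 3), the formula needs 49 patients and power at 50 is Φ(0.4339 × √47 − 1.645) = Φ(1.330) = 0.908. The stated 50 patients and 90% are reproduced.

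**Step 2: see what skew would do.** The one-sided 5% z test with Lin's variance was simulated at n = 50, with 40,000 trials per cell and the true CCC held at 0.60 or 0.81. Two models were used, with s the log-SD:

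- Model A: both devices lognormal with equal margins, log-scale correlation r = ln(1 + CCC(exp(s²) − 1)) / s². All values stay positive.
- Model B: a lognormal true value with variance v, plus independent normal error on each device with variance v(1 − CCC)/CCC. This produces negative values, which the indices cannot take: about 1–5% of values at s = 0.5 and 18–26% at s = 1.0.

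Type I error at CCC 0.60 / power at CCC 0.81:

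| Assumed shape | Model A | Model B |
|---|---|---|
| s = 0.25 | 5.6% / 89% | 5.5% / 89% |
| s = 0.5 | 8.7% / 86% | 8.1% / 81% |
| s = 0.8 | 15% / 81% | 11% / 67% |
| s = 1.0 | 19% / 79% | 12% / 55% |

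Normal data gave 4.7% / 91%. Under model A, a device at 0.81 is missed 14% to 21% of the time at s = 0.5 to 1.0. The 55% cell of model B is an outer bound only, because of its impossible values.

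**Step 3: see what a different interval would do.** A percentile bootstrap one-sided 95% lower bound, compared with 0.60 (20,000 trials of 1,000 resamples), gave:

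| Assumed shape | Model A | Model B |
|---|---|---|
| s = 0.25 | 4.5% / 89% | 4.4% / 86% |
| s = 0.5 | 4.7% / 84% | 3.0% / 72% |
| s = 0.8 | 5.2% / 76% | 1.5% / 42% |
| s = 1.0 | 5.4% / 72% | 0.7% / 23% |

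Normal data gave 4.8% / 90%. With 10–30% exact zeros shared by both devices, and model A elsewhere at s = 0.5 or 1.0, the bootstrap error was 7–11%. At 30% zeros and s = 0.5 it was 10.9%, against 10.1% for the z test.

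**Step 4: compare with what the protocol prescribes.** The z test appears only in the sample-size paragraph. Section 11.1 asks for a graph, a coefficient and its band. The error rates in step 2 therefore apply only if the sizing test is also used as the analysis, which the protocol does not say.

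**The case for a change.** The strongest case for a change is that the loss does not hang on one model. With gamma and zero-censored shapes added, and a wider range of log-SDs, simulated power ran from 0.69 to 0.87 and type I error from 0.07 to 0.23. If the z test's critical value is reset to hold 5% error, power at n = 50 under model A falls to about 0.83 at log-SD 0.4, 0.70 at 0.6 and 0.56 at 0.8. Error inflation matters most: a device that only reaches the protocol's own null value would pass too often. Qualifying the power statement would cost a few words.

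What stands is that the 90% depends on approximate bivariate normality and that neither place says so. The rest does not carry a change:

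- The size of any shortfall comes wholly from assumed shapes. A lower bound at zero does not by itself imply strong skew, and the remark on non-normal data in section 11.1 is a general reporting rule that names no index.
- The power statement is not bare. Section 11.2 gives test, tail, level and both CCC values; the synopsis only abridges it. In a text translated as roughly as this one, the word for guaranteeing is weak evidence of an absolute promise.
- A bootstrap bound is a trade-off. It controls error under continuous skew, but it can be very conservative with low power (model B), and it exceeds 5% when zeros are shared.

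**Conclusion.** The concern is right about the mathematics, but it does not call for a change. The 50 patients and 90% are correctly computed under the ordinary basis for sizing a CCC study. A statistician reading a z test on a CCC will understand that it is a normal-theory calculation. Writing that assumption down would change no patient number, no analysis and no conclusion.

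If the zero-bounded indices prove clearly skewed (log-SD 0.5 to 1.0, model A), realised power with the sizing test would be about 79–86% and its error about 9–19%. With log-SD 0.25 both stay close to the stated values. Nothing in the protocol says which case applies, and less skewed parameters such as mean heart rate may come close to 90%. The interval method for the CCC is an ordinary choice for a statistical analysis plan. Section 11.1 leaves it open, and a robust interval there would contradict nothing in the protocol.
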